### **6.3. Other Efficacy Endpoints**

#### **6.3.1. Definition of Other Efficacy Endpoints**

Other efficacy endpoints that will be performed for All LEN Analysis are provided below.

- Change from baseline in HIV 1 RNA (copies/mL) by visit
- Change from baseline in CD4 cell count (/uL) by visit
- Proportion of participants with HIV 1 RNA < 50 copies/mL by visit based on Missing = Failure and Missing = Excluded analyses

#### **6.3.2. Analysis of Other Efficacy Endpoints**

Baseline and the change from baseline in HIV-1 RNA ( $\log_{10}$  copies/mL) and CD4 cell count (/uL) by visit for All LEN Analysis will be summarized using descriptive statistics.

Mean  $\pm$  95% CI of the change from baseline in HIV-1 RNA ( $\log_{10}$  copies/mL) will be plotted by visit.

Number and percentage of participants with HIV-1 RNA < 50 copies/mL by visit will be analyzed using the following analyses:

- Missing = Failure (M = F):

In this approach, missing data will be treated as virologic failure and summarized into the “missing” category (see list of HIV-RNA categories below). The denominator for percentages at a visit is the number of participants in the FAS, excluding ongoing participants who have missing HIV-1 RNA at a visit and have not reached the upper limit of the analysis window for the corresponding visit and participants who have missing HIV-1 RNA at a visit and have completed the study before reaching the upper limit of the analysis window for the corresponding visit.

- Missing = Excluded (M = E):

In this approach, missing data will be excluded in the computation of the percentages (ie, missing data points will be excluded from both the numerator and denominator in the computation). The denominator for percentages at a visit is the number of participants in the FAS with nonmissing HIV-1 RNA value at that visit.

No statistical testing is planned. The number and percentage of participants with HIV-1 RNA in the following categories will be summarized:

- < 50 copies/mL
  - < 20 copies/mL
    - < 20 copies/mL Not Detectable
    - < 20 copies/mL Detectable
  - 20 to < 50 copies/mL
- 50 to < 200 copies/mL
- 200 to < 400 copies/mL
- 400 to < 1000 copies/mL
- $\geq$  1000 copies/mL
- Missing (only applicable to M = F analysis)

Analysis of the other efficacy endpoints will be based on the FAS.

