- Cohort 2 participants will receive SC LEN 927 mg at the Day 1 SC visit while continuing on their OBR (14 days after the first dose of oral LEN). Participants will continue to receive SC LEN 927 mg every 6 months (26 weeks) \pm 2 weeks from last injection thereafter while continuing their OBR.
- SC study drug administration will occur at the study center without regard to food.
- Provide ISR assessment worksheet and instruct the participants to measure and report ISRs following the administration of the SC injections.
- For all participants on oral weekly bridging, the first dose of oral LEN will be administered at the study center without regard to food and up to 2 bottles will be provided to the participant with instructions to take the remaining doses at home once a week (1 \times 300 mg LEN) without regard to food on the same day of the week that the first dose was given.
- Document study drug administration.
- Document study drug accountability.
- Participants who meet the criteria for virologic failure will be managed according to the Management of Virologic Failure Section 6.7.

The Week 156 visit and visits every 26 weeks thereafter are to be completed within \pm 2 weeks of the protocol-specified visit date. Each SC LEN dosing should occur within 26 weeks \pm 2 weeks of the previous SC LEN dosing.

The following procedures are to be completed at all visits unless otherwise noted.

- Review of AEs and changes in concomitant medications.
- Symptom-directed physical examination.
- Obtain vital signs and body weight.
- Obtain blood and urine samples as noted in Section 6.5.
- SC study drug administration will occur at the study center without regard to food.

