## 1. INTRODUCTION

This statistical analysis plan (SAP) describes the statistical analysis methods and data presentations to be used in tables, figures, and listings (TFLs) of the Year 2 and Year 3 analyses for Study GS-US-200-4625. The Year 2 and Year 3 analysis will be performed when all participants in both cohorts have had HIV-1 RNA data in the Week 104 and Week 156 analysis windows, respectively (or reached the upper limit of the corresponding analysis window with missing HIV-1 RNA data), or prematurely discontinued or completed the study drug.

This SAP is based on the study protocol amendment 4 dated 18 January 2023 and the electronic case report form (eCRF). The SAP will be finalized prior to data finalization for the Year 2 analysis.

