**Table 3-1. Analysis Windows for All LEN Analysis**

Analysis Visit	Nominal Study Day	Analysis Window Study Day Range	
		HIV-1 RNA and Vital Signs	Hematology, (Urine) Chemistry, Urinalysis, CD4 Cell Count, and CD4%
Baseline		≤ First Dose Date, if time not available ≤ First Dose Date/Time, if time available	≤ First Dose Date, if time not available ≤ First Dose Date/Time, if time available
Day 1 (Postdose) a	1	> First Dose Date/Time, 1	> First Dose Date/Time, 1
Day 2	2	2, 5	NP
Day 8	8	6, 11	2, 11
Day 1 SC	15	12, 29	12, 29
Week 4	43	30, 64	30, 64
Week 10	85	65, 106	65, 106
Week 16	127	107, 148	107, 148
Week 22	169	149, 183	149, 183
Week 26	197	184, 232	184, 232
Week 36	267	233, 323	233, 323
Week 52	379	324, 414	324, 414
Week 62	449	415, 505	415, 505
Week 78	561	506, 596	506, 596
Week 88	631	597, 687	597, 687
Week 104	743	688, 778	688, 778
Week 114	813	779, 869	779, 869
Week 130	925	870, 960	870, 960
Week 140	995	961, 1051	961, 1051
Week 156	1107	1052, 1142	1052, 1142
Week 166	1177	1143, 1233	1143, 1233
Week 182	1289	1234, 1324	1234, 1324
Week 192	1359	1325, 1415	1325, 1415
Week 208	1471	1416, 1506	1416, 1506

NP = Not planned by the protocol

a Day 1 postdose will be used to label the records collected on Day 1 with collection time after the Day 1 dosing time. The Day 1 postdose will be used in listings to identify such records. Day 1 postdose visit will not be included in by-visit table summary

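### The by-visit Missing = Failure rule in SAP 6.3.2 has no exclusion for windows in which no sample was planned, so after the protocol's move to 26-weekly visits at Week 156 it can score suppressed participants as failures

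*SAP*

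**What the plan says.** SAP 1 gives its basis: "This SAP is based on the study protocol amendment 4 dated 18 January 2023". SAP Appendix 1 accordingly has visits after Week 52 alternating every 10 and 16 weeks, with no change at Week 156. SAP Table 3-1 ("Analysis Windows for All LEN Analysis") has rows for Weeks 156, 166, 182, 192 and 208.

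SAP 6.3.1 lists the proportion with HIV-1 RNA < 50 copies/mL "by visit based on Missing = Failure and Missing = Excluded analyses". For M = F, SAP 6.3.2 says: "In this approach, missing data will be treated as virologic failure", with such values shown in a Missing category. The denominator is the Full Analysis Set with two exclusions:

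- "excluding ongoing participants who have missing HIV-1 RNA at a visit and have not reached the upper limit of the analysis window"
- "participants who have missing HIV-1 RNA at a visit and have completed the study before reaching the upper limit of the analysis window"

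SAP Appendix 3, item 8 makes the first exclusion a calendar test: the study day at data finalization is compared with the upper limit of the window.

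The current protocol (6.3.2) has a different schedule: "The Week 156 visit and visits every 26 weeks thereafter are to be completed within" 2 weeks either side of the target date. Protocol 3.4 and 6.3.2 make this depend on regulatory or ethics approval and on re-consent. Protocol Appendix 2 (note bb) recommends only a phone contact for adverse events between the clinic visits after Week 156.

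**The concern.** M = F is reasonable when a missing value means that a planned sample was not obtained. It is not reasonable when no sample was planned, because the failure then comes from the calendar and says nothing about the participant. Neither exclusion in SAP 6.3.2 asks whether a visit was due in the window. A participant who is on lenacapavir, suppressed and attending every visit can therefore be counted as not suppressed at a time when the protocol did not ask for a sample.

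What is at stake is how the late rows of a long-term virologic table are read. At the Year 3 analysis every continuing participant has reached the end of the Week 156 window, and those who started earlier may be well past it, so rows after Week 156 can be populated. A lower percentage there could be taken as loss of response.

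**Working it through.** **Inputs.** Windows: SAP Table 3-1. Study Day counted from first lenacapavir dose: SAP 3.8.1. Day 1 SC is 14 days after first oral dose, and visit allowances are ±6 days after Week 52 and ±2 weeks from Week 156: protocol 6.3.2. Participants enrolled, 72: protocol 1.2.2.2. Participants remaining at Amendment 5, 13: protocol Appendix 7.

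**1. Reproduce Table 3-1.** Nominal day = 14 + 7 × week + 1. Week 166: 14 + 1162 + 1 = 1177. Week 192: 14 + 1344 + 1 = 1359. Weeks 156, 182 and 208 give 1107, 1289 and 1471. Window limits are midpoints between neighbouring nominal days: (1107 + 1177)/2 = 1142, (1177 + 1289)/2 = 1233, (1289 + 1359)/2 = 1324 and (1359 + 1471)/2 = 1415. The Week 166 window is therefore 1143-1233 and the Week 192 window 1325-1415, exactly as printed. The table is correct for the alternating schedule.

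**2. Place both schedules in the windows, without oral bridging.**

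| Visit | Alternating, ±6 days | 26-weekly, ±14 days | Window |
|---|---|---|---|
| Week 156 | 1101-1113 | 1093-1121 | 1052-1142 |
| Week 166 | 1171-1183 | none | 1143-1233 |
| Week 182 | 1283-1295 | 1275-1303 | 1234-1324 |
| Week 192 | 1353-1365 | none | 1325-1415 |
| Week 208 | 1465-1477 | 1457-1485 | 1416-1506 |

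On the alternating schedule every window is filled. On the 26-weekly schedule the Week 166 and Week 192 windows are empty by design. The first phone contact, 13 weeks after Week 156, is at Week 169 = 14 + 1183 + 1 = Day 1198. It lies inside the Week 166 window, and no sample is planned.

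**3. Apply the M = F rule.** Take an ongoing, suppressed participant on the 26-weekly schedule with no bridging, past Day 1233 and with no unscheduled sample. The first exclusion fails because the upper limit has been passed. The second fails because the participant has not completed the study. The participant stays in the denominator, counts as a failure and appears in the Missing row. The same happens at Week 192 after Day 1415.

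**4. Add oral bridging.** Protocol weeks leave out bridging periods (protocol 6.3.2), while Study Day counts them (SAP 3.8.1). With b days of bridging, the Week 156 visit falls on Day 1107 + b and the Week 182 visit on Day 1289 + b. For b = 36 these are Days 1143 and 1325; for b = 126 they are Days 1233 and 1415. So, on nominal days, 36 to 126 days of bridging put the Week 156 visit in the Week 166 window and the Week 182 visit in the Week 192 window. The Week 182 window (1234-1324) is then the one with no scheduled sample.

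**5. Size.** With k affected participants and M = F denominator D, the < 50 copies/mL percentage loses 100 × k/D points. The documents give neither k nor D. I take k from 0 to 13, and D = 72 (all enrolled) or D = 36 as illustrations.

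| k | D = 72 | D = 36 |
|---|---|---|
| 0 | 0 | 0 |
| 1 | 1.4 | 2.8 |
| 5 | 6.9 | 13.9 |
| 13 | 18.1 | 36.1 |

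**The case against.** The case for leaving this alone has real weight.

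- The SAP states its Amendment 4 basis openly, and Table 3-1 agrees with the SAP's own visit schedule. That is so, but the same SAP governs the Year 3 analysis, its 6.5 plans no change, and its revision table is empty.
- The 26-weekly schedule is conditional. Anyone who passed a window before local approval and re-consent had a visit planned in it. This stands, and it means that k may be zero.
- The display is an other efficacy endpoint, descriptive and untested. Missing has its own row, and a Missing = Excluded version sits alongside. This stands and limits the importance. The M = F percentage below 50 copies/mL still falls.
- Rebound confirmation visits and other unscheduled samples can fill a window. This stands and lowers k further.

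Two stronger readings are tempting. One is that the long-term curve will drop at Week 166, recover at Week 182 and drop again at Week 192, with all 13 remaining participants failing and then recovering. The documents do not support this. They give no dates of re-consent or data cut; 13 is not the M = F denominator, because participants who stopped early stay in it; bridging moves the empty windows; and the only plot specified in SAP 6.3.2 is mean change in HIV-1 RNA. The other is that the Week 166 and Week 192 rows should simply be deleted. For a participant with 36 to 126 days of bridging, that would discard real samples and leave the falsely empty Week 182 row in place.

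**Conclusion.** The point holds in a conditional and limited form. The M = F rule as written scores an ongoing, suppressed participant as a failure in any window after Week 156 in which the protocol planned no sample and none was taken. Without bridging those windows are Weeks 166 and 192; with bridging they can be others, such as Week 182.

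Between 0 and 13 participants are affected. The upper bound assumes that all those remaining at Amendment 5 moved to the 26-weekly schedule before these windows and were past them at the data cut. The loss is k/D, so the percentages in the working are illustrations, not estimates.

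A reader might infer that the trial's main results are at risk. They are not. The primary endpoint belongs to the 14-day randomized period, and the schedule change removes no visit at or before Week 156, so it does not reach the Week 104 and Week 156 snapshot endpoints. The correction is worth making because it is cheap and prevents a schedule artefact from being read as loss of suppression.

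**What to change.** Update the basis in SAP 1 and the schedule in SAP Appendix 1 to the current protocol. Then add one rule to SAP 6.3.2: for windows after Week 156, an ongoing participant with no HIV-1 RNA result in the window, and no sample scheduled in it, is left out of both the M = F denominator and the Missing row. Whether a sample was scheduled is judged by the visit schedule the participant was on, with bridging time taken into account. A simpler alternative is to end the by-visit M = F display at Week 156.

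Keep the Table 3-1 windows as they are. Samples that fall in the Week 166 or Week 192 windows are then still used. Recomputing midpoints without those two rows would extend the Week 156 window to (1107 + 1289)/2 = Day 1198, against Days 1052-1142 in protocol 8.5.2.

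No new assessments are needed. The first option does need a per-participant date of switching to the 26-weekly schedule, which the SAP does not now define; the alternative avoids this but gives up the later M = F rows.

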#### **6.4. Subgroup Analysis**

Analysis of subgroups (defined in Section 3.4.1) will be performed for the proportion of participants with HIV-1 RNA < 50 copies/mL at Weeks 104 as determined by the US FDA-defined snapshot algorithm. Subgroup analysis will be performed on FAS for All LEN Analysis set for participants who receive at least 1 dose of SC injection. Results will be descriptive without statistical testing. The 95% CIs of the proportions will be provided using the exact method.

#### **6.5. Changes from Protocol-Specified Efficacy Analyses**

No change from protocol-specified efficacy analysis is planned.

## **7. SAFETY ANALYSES**

For participants who discontinue from the oral bridging of LEN, only data collected up to 60 days after Last Dose Date of Oral Bridging will be included. All data collected will be included in data listings.

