6.4. Posttreatment Assessments

6.4.1. Early Termination Visit Assessments

6.4.1.1. Early Termination Visit After Day 1 and Prior to Day 1 SC

If a participant discontinues oral LEN or decides not to initiate SC LEN at Day 1 SC, an early termination visit should be performed within 72 hours of decision to discontinue the study drug. Participants in Cohort 1 will be asked to continue to attend study visits until completion of the Functional Monotherapy Period. Participant will be required to complete the 90-day follow-up visit. Refer to Section 6.4.2.

6.4.1.2. Early Termination Visit After Day 1 SC and Prior to Week 52

If a participant decides to discontinue SC LEN prior to Week 52, an early termination visit should be performed within 72 hours of decision to discontinue study drug.

The participant will be asked to continue attending the scheduled study visits through the Week 52 visit.

- If the participant decides to discontinue SC LEN and agrees to continue to attend study visits through Week 52, no follow-up visits are required.
- If the participant decides to discontinue SC LEN and does not agree to continue to attend study visits through Week 52, the 30-day, 90-day, and 180-day follow-up visits are required. Refer to Section 6.4.2. The 180-day follow-up may be conducted via a phone call per the investigator's discretion.

6.4.1.3. Early Termination Visit After Week 52

If a participant continues the study after completing the Week 52 visit, but discontinues SC LEN prior to study completion, an early termination visit should be performed.

- If the participant discontinues LEN (SC and oral) and continues to attend study visits through their next SC dosing visit, all assessments, except SC dosing, will be performed at the last visit. No further follow-up visits are required.
- If the participant discontinues SC LEN and does not continue to attend study visits through the participant's next SC dosing visit, the 30-day, 90-day, and 180-day follow-up visits are required. Refer to Section 6.4.2. The 180-day follow-up may be conducted via a phone call per the investigator's discretion.
- If a participant discontinues oral LEN during the Oral Bridging Period and does not continue to attend study visits through their next SC dosing visit, the participant will be required to complete the 90-day follow-up visit (see Section 6.4.2).

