If there are any abnormal laboratory results with a possible or probable causal relationship with the study drug, every attempt should be made to keep the participant in the study and repeat those laboratory tests weekly (or as often as deemed prudent by the investigator) until the abnormality is resolved, returns to baseline, or is otherwise explained. If this is not possible or acceptable to the participant or investigator, the participant may be withdrawn from the study.

If there are any AEs, every attempt should be made to keep the participant in the study and should be followed up until the AE is resolved or stable. Gilead may request that certain AEs be followed beyond the protocol-defined follow-up period. If this is not possible or acceptable to the participant or investigator, the participant may be withdrawn from the study.

The following evaluations should be performed at the early termination visit:

- Review of AEs and changes in concomitant medications.
- Symptom-directed physical examination (urogenital/anorectal examinations will be performed at the discretion of the investigator).
- Vital signs measurement (blood pressure, pulse, respiration rate, and temperature).
- Obtain blood and urine samples as noted in Section 6.5.
- Counsel participant regarding the importance of continuing a complete ART regimen in accordance to standard of care, and refer patient to an appropriate HIV treatment facility.

6.4.2. 30-Day, 90-Day, and 180-Day Follow-Up Visits

The assessments below will be completed for participants who are required to complete 30-day, 90-day, and/or 180-day follow-up visits as noted in Section 6.4.1. Follow-up visits will be scheduled based on the date of the early termination visit. No follow-up visits are required for those participants who do not receive SC LEN at the Week 52 visit.

For scheduling the follow-up visits, a \pm 6-day window may be used.

The following evaluations are to be completed at the follow-up visits:

- Review of AEs and changes in concomitant medications.
- Symptom-directed physical examination.
- Vital signs measurement (blood pressure, pulse, respiration rate, and temperature), including weight.
- Obtain blood and urine samples as noted in Section 6.5.

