8.6. Safety Analysis

All safety data collected on or after the date that study drug was first dispensed will be summarized by cohort and treatment (according to the study drug received). For participants who discontinue from the oral LEN, only data collected up to 60 days (approximately 5 times the LEN oral dose half-life) after the last dose of the oral tablet will be included. All data collected will be included in data listings.

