The inclusion of female born participants of childbearing potential requires using at least an acceptable effective contraceptive. They must have a negative serum pregnancy test at screening and a negative pregnancy test at the Day 1 visit prior to the dose of study drug. Pregnancy tests will be performed as defined by the Study Procedures Table ([Appendix 2](#)). In the event of a delayed menstrual period (over 1 month between menstruations), a pregnancy test must be performed to rule out pregnancy. This is also applicable for female born participants of childbearing potential with infrequent or irregular periods.

Duration of contraception for female born participants of childbearing potential enrolled in this clinical trial should start from screening visit until 60 days after the last dose of oral study drug or 700 days following the last dose of subcutaneous (SC) study drug, whichever is later, as applicable.

Female born participants of childbearing potential must agree to 1 of the following contraceptive methods:

Complete abstinence from intercourse of reproductive potential. Abstinence is an acceptable method of contraception only when it is in line with the participant's preferred and usual lifestyle.

Or

- Consistent and correct use of 1 of the following methods of birth control listed below:
 - Hormonal and nonhormonal intrauterine device (IUD)
 - Bilateral tubal occlusion sterilization (upon medical assessment of surgical success)
 - Vasectomy in the male born partner (upon medical assessment of surgical success)

Or

Female born participants who initiate use of a hormonal contraceptive > 7 days after onset of menses as one of their birth control methods should use additional back-up contraception (eg, condoms) or avoid sexual intercourse for 7 days. Hormonally-based contraceptives and barrier methods permitted for use in this protocol are as follows:

— Hormonal Methods

- Oral contraceptives (either combined or progesterone only)
- Injectable progesterone^a
- Subdermal contraceptive implant^a
- Transdermal contraceptive patch^a
- Contraceptive vaginal ring^a

— Barrier methods

- Male condom (with or without spermicide)
- Female condom (with or without spermicide)
- Diaphragm with spermicide^a

- Cervical cap with spermicide^a
- Sponge with spermicide

^a Not approved in Japan.

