#### **7.1.5. Treatment-Emergent Adverse Events**

##### **7.1.5.1. Definition of Treatment-Emergent Adverse Events**

The TEAEs are defined as any AEs that begin on or after the date of first dose of study drug or any AEs leading to premature discontinuation of study drug. For participants who discontinue from the oral bridging of LEN, only AEs collected up to 60 days after the Last Dose Date of Oral Bridging will be considered treatment emergent.

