### **7.2.2.1. Treatment-Emergent Laboratory Abnormalities**

Treatment-emergent laboratory abnormalities are defined as values that increase at least 1 toxicity grade from baseline at any postbaseline visit (and up to 60 days after Last Dose Date of Oral Bridging if participants discontinue from the oral bridging of LEN). If the relevant baseline laboratory value is missing, any abnormality of at least Grade 1 observed at any postbaseline visit will be considered treatment emergent.

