## **7.8. Changes from Protocol-Specified Safety Analyses**

No change from protocol-specified safety analyses is planned.

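### SAP Section 7 ends safety tables 60 days after the last bridging tablet, applying an oral half-life rule to participants who have all had SC LEN and leaving out a required 90-day visit

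*SAP*

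**What the plan says.** SAP Section 7 states, for participants who discontinue from oral bridging, that "only data collected up to 60 days after Last Dose Date of Oral Bridging will be included". SAP 7.1.5.1 repeats this for adverse events: "only AEs collected up to 60 days after the Last Dose Date of Oral Bridging will be considered treatment emergent". SAP 7.2.2.1 repeats it for laboratory abnormalities: "up to 60 days after Last Dose Date of Oral Bridging if participants discontinue from the oral bridging of LEN". None of these sections sets a limit for participants who stop directly from SC LEN, or for those who stop during the initial oral lead-in.

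The rule starts in the protocol. Section 8.6 reads: "For participants who discontinue from the oral LEN, only data collected up to 60 days (approximately 5 times the LEN oral dose half-life". Sections 8.6.2 and 8.6.3 apply the same 60 days to treatment-emergent adverse events and laboratory abnormalities. The protocol wording covers oral LEN in general, whereas the SAP covers bridging only. SAP 7.8 nevertheless says: "No change from protocol-specified safety analyses is planned".

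On follow-up, Protocol 6.4.1.3 covers participants who stop oral LEN during bridging after Week 52 and do not attend through their next SC dosing visit: "the participant will be required to complete the 90-day follow-up visit (see Section 6.4.2". Protocol 6.4.2 fixes the timing: "Follow-up visits will be scheduled based on the date of the early termination visit", with a window of 6 days either side. That visit includes adverse event review and blood and urine samples.

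**The concern.** A limit built on the oral half-life suits someone who has taken only tablets. Bridging replaces a missed SC injection (Protocol 5.4), so everyone who stops from bridging has also had the long-acting form. Two participants with the same SC history are then handled differently: the one who took a bridging tablet is cut at 60 days and the other is not cut at all.

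The trial also asks the first participant to return for a visit whose results the tables cannot use. The effect runs one way. Dropping late records can only lower the number of participants shown with an adverse event or a laboratory abnormality. In a small study with descriptive safety tables, a few omitted participants could be visible.

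**Working it through.** **1. The plan's own figure.** The protocol gives 60 days as about five oral half-lives, which implies 60 / 5 = 12 days. Neither document states the oral half-life, so the 60 days cannot be reproduced independently. Neither states an SC half-life.

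**2. Who is cut.**

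| Participant stops LEN | Has had SC LEN | Protocol 8.6 | SAP 7 |
|---|---|---|---|
| In the oral lead-in, before any injection | No | 60 days | No limit |
| Directly from SC LEN | Yes | No limit | No limit |
| From oral bridging | Yes | 60 days, read as oral LEN | 60 days |

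The SAP keeps the limit only in the row where every participant has had SC LEN. It drops it in the one row that the oral half-life argument fits.

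**3. When the 90-day visit falls.** Let g be the days from the last bridging tablet to the early termination visit, with g at least 0. The visit lies between g + 90 − 6 and g + 90 + 6.

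- g = 0: Days 84 to 96 after the last tablet, which is 84 − 60 = 24 to 96 − 60 = 36 days past the cut.
- g = 7: Days 91 to 103.
- To be retained, the visit would need g + 84 ≤ 60, which is impossible.

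Where the 30-, 90- and 180-day visits all apply, at g = 0 the 30-day visit (Days 24 to 36) is kept. The 90-day visit and the 180-day visit (Days 174 to 186) are lost.

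**4. Where the cut lies relative to the last injection.** Bridging normally starts 26 to 28 weeks after it (182 to 196 days). With almost no bridging the cut falls at 182 + 60 = 242 to 196 + 60 = 256 days. With 12 weeks of bridging it falls at 182 + 84 + 60 = 326 to 196 + 84 + 60 = 340 days. These are illustrations, not bounds: Protocol 5.4 also covers later starts and bridging beyond 12 weeks.

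**5. Which records drop out.** Laboratory results drawn at the 90-day visit leave the summary tables. So do adverse events with onset after Day 60. An event with onset by Day 60 that is first reported at the 90-day visit is ambiguous: the SAP speaks of events collected by then, while Protocol 8.6.2 summarizes by onset date. Listings keep everything (SAP 7), and SAP 7.1.6.1 keeps all deaths in the high-level summary.

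**6. Conflicts inside the SAP.** SAP 7.2 says that laboratory summaries use all data available at the database snapshot, which does not fit the cut. SAP 4.3 cites the drug's long-acting nature and counts study duration to the last study date, which by SAP 3.8.1 includes the follow-up visits. Reported duration can therefore include time in which new events are not counted.

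**The case against.** The best defence is that the SAP follows the protocol. Someone who stops oral LEN during bridging fits the wording of Protocol 8.6, so the length of the cut is not a SAP deviation. The SAP's own departure, leaving lead-in discontinuers uncut, brings in more data rather than less. Both points stand. The undeclared change is a reporting fault in SAP 7.8, not a source of under-counting.

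A 90-day visit alongside a 60-day limit is also not peculiar to bridging. Protocol 6.4.1.1 requires the same visit of participants who stop oral LEN before any injection. The mismatch of 60 and 90 days is therefore not enough by itself. What remains is that the oral rationale does not reach people with SC exposure, and that SC-exposed participants are treated unequally.

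Three stronger readings are tempting.

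- A reader might infer that late safety data are lost. They are not: listings hold all data and the overall summary holds all deaths.
- A reader might compare the cut with the contraception period in Protocol Appendix 4, "60 days after the last dose of oral study drug or 700 days following the last dose of subcutaneous (SC) study drug", and conclude that it covers only 242 / 700 = 35% to 340 / 700 = 49% of the exposed time. The 700 days serve contraception and pregnancy reporting. They show that the protocol regards SC exposure as much longer than oral exposure, but they are not a safety-analysis window or a measured depot duration.
- A reader might take it as established that drug is present at the cut. Protocol 1.2.2.1 reports mean concentrations above target through 26 weeks (182 days) after an injection. Nothing in the documents describes Days 242 to 340.

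**Conclusion.** The point holds as a fault of consistency shared by both documents. A limit justified by the oral half-life is applied to participants who have all had SC LEN, while those who stop directly from SC LEN have none. For those who stop during bridging after Week 52 and leave, the one required follow-up visit falls at least 24 days past the limit.

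The effect on results is unknown. Protocol 1.2.2.2 gives 72 participants enrolled, but neither document says how many stopped from bridging; the number may be small or zero. Participants who resumed SC LEN are not affected.

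This rests on two assumptions. The early termination visit is not before the last tablet. Section 8.6 also read the same under protocol amendment 4, on which the SAP says it is based; the amendment 5 change list shows no change to that section.

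**What to change.** In SAP 7, 7.1.5.1 and 7.2.2.1, remove the 60-day limit for any participant with at least one SC LEN injection and include data through the last study date, as for those who stop directly from SC LEN. Since every bridging participant has had an injection, this amounts to deleting the three clauses. Make SAP 7.2 agree.

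Leave oral lead-in discontinuers uncut, as the SAP has them now. Restoring the protocol limit for them would remove their own 90-day visit from the tables.

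List both departures from Protocol 8.6 in SAP 7.8: no limit after lead-in discontinuation, and no limit after bridging.

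The cost is wording and a date filter, with no new data collection. The downside is that a few more late events, some possibly after a switch to other therapy, would count as treatment emergent.
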